3.3 Early Withdrawal of Subjects

3.3.1 Criteria for removal from study

Insert subject withdrawal criteria (e.g., safety reasons, failure of subject to adhere to protocol requirements, subject consent withdrawal, disease progression, etc.).

Participant consent withdrawal and safety reasons will be criterion for removal from the study.

3.3.2 Follow-up for withdrawn subjects

Describe when and how to withdraw subjects from the study; the type and timing of the data to be collected for withdrawal of subjects; whether and how subjects are to be replaced; the follow-up for subjects withdrawn from investigational treatment.

Participants may withdraw consent at any time, we will utilize all data collected up to that point. As time allows (~12 month pilot period maximum), we will recruit additional participants for the pilot.

4.0 Recruitment Methods

- Upload recruitment materials for your study in CATS IRB (<http://irb.psu.edu>). **DO NOT** include the actual recruitment wording in this protocol.
- StudyFinder: If StudyFinder (<http://studyfinder.psu.edu>) is to be used for recruitment purposes, separate recruitment documents do not need to be uploaded in CATS IRB. The necessary information will be captured from the StudyFinder page in your CATS IRB study.
- Any eligibility screening questions (verbal/phone scripts, email, etc.) used when contacting potential participants must be uploaded to your study in CATS IRB (<http://irb.psu.edu>).

[Do not type here]

4.1 Identification of subjects

Describe the source of subjects and the methods that will be used to identify potential subjects (e.g., organizational listservs, established recruitment databases, subject pools, medical or school records, interactions during a clinic visit, etc.). If not recruiting subjects directly (e.g., database query for eligible records or samples) state what will be queried, how and by whom.

StudyFinder:

- If you intend to use StudyFinder (<http://studyfinder.psu.edu>) for recruitment purposes, include this method in this section.
- Information provided in this protocol needs to be consistent with information provided on the StudyFinder page in your CATS IRB study.

For Penn State Health submissions using Enterprise Information Management (EIM) for recruitment, and for non-Hershey locations as applicable, attach your EIM Design Specification form on in CATS IRB (<http://irb.psu.edu>). See “HRP-103- Investigator Manual, What is appropriate for study recruitment?” for additional information. **DO NOT** include the actual recruitment material or wording in this protocol.

Participants meeting inclusion/exclusion criteria will be those participating in the NFP program through the Geisinger Clinic or UPMC Home Healthcare of Central PA. Potential participants who are <28 weeks' gestation and at least five potential participants who have used nicotine containing products in the past 3 months will be identified by visiting nurses and/or their supervisors.

4.2 Recruitment process

Describe how potential subjects first learn about this research opportunity or indicate as not applicable if subjects will not be prospectively recruited to participant in the research. Subject recruitment can involve various methods (e.g., approaching potential subjects in person, contacting potential subjects via email, letters, telephone, ResearchMatch, or advertising to a general public via flyers, websites, StudyFinder, newspaper, television, and radio etc.). **DO NOT** include the actual recruitment material or wording in this protocol.

[Do not type here]

4.2.1 How potential subjects will be recruited.

Potential participants will be recruited through established partnerships with Geisinger and UPMC Nurse Family Partnership agencies. After potential participants are identified by visiting nurses and/or their supervisors, visiting nurses will share information about the pilot study verbally and through a written summary handout prepared by the study team.

4.2.2 Where potential subjects will be recruited.

Potential participants will be recruited in their own homes during regularly scheduled home visits with their NFP visiting nurse.

4.2.3 When potential subjects will be recruited.

Potential participants will be recruited during pregnancy (<28 weeks' gestation) during regularly scheduled home visits with their visiting nurse from NFP.

4.2.4 Describe the eligibility screening process and indicate whether the screening process will occur before or after obtaining informed consent. Screening begins when the investigator obtains information about or from a prospective participant in order to determine their eligibility. In some studies, these procedures may not take place unless HIPAA Authorization is obtained OR a waiver of HIPAA Authorization when applicable for the screening procedures is approved by the IRB. [For FDA regulated studies, consent for any screening activities would need to be obtained prior to screening unless specifically waived by the IRB.]

All NFP visiting nurses participating in this study will be trained in screening procedures. No Protected Health Information (PHI) will be collected during screening procedures. Potential participants will be approached by NFP visiting nurses during regularly scheduled home visits. NFP visiting nurses will provide recruitment materials that include information about the study with potential participants and verbal consent will be obtained before any screening questions are asked of participants. Once a potential participant is deemed eligible after screening and expresses interest in participating, written informed consent will be obtained. Information collected as part of screening procedures will only be used to assess eligibility and will not be used in research analyses.

****Site Congruency: Is the information provided in the above section (Recruitment Methods) consistent across all relying sites in this research?**

Yes

No - Identify the sites that have dissimilar procedures: *[This field should solely identify the site. Dissimilar procedures across sites should be identified in the SITE workspace via HRP-XXX – R2S Site Plan]*
[Type protocol text here]

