1.0 Objectives

1.1 Study Objectives

Describe the purpose, specific aims or objectives. State the hypotheses to be tested.

Aim 1: To add a cardiovascular health (CVH) module to the existing perinatal home visitation program delivered by Nurse Family Partnership (NFP) visiting nurses in the Northern Appalachian region of Central Pennsylvania.

Aim 2: To train selected NFP visiting nurses on the CVH module and assess the acceptability of the module as well as the fidelity of delivery to pregnant and postpartum women.

Aim 3: To demonstrate the feasibility of enrolling and following pregnant women participating in the NFP program into a pilot research study evaluating a CVH module delivered as part of the existing NFP program.

Aim 4: To develop an activity protocol during and after pregnancy to decrease sedentary behavior during and after pregnancy and increase activity level during the postpartum period.

Aim 5: To pilot the use of digital devices to encourage and monitor activity and associated biometric outcomes, primarily blood pressure and actigraphy.

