3.1 Inclusion Criteria

Create a numbered list of the inclusion criteria that define who will be included in your final study sample (e.g., age, gender, condition, etc.)

1. Enrolled in and receiving the Nurse-Family Partnership program through the Geisinger Clinic or UPMC Home Health Care of Central PA
2. Age \geq 18 years old
3. Nulliparous pregnant woman
4. Women with a singleton viable pregnancy confirmed by NFP home visitors
5. English speaking
6. Access to reliable internet service required for data collection
7. Willingness to download and access an app on personal smartphone
8. A minimum of 5 women with use of nicotine containing products (cigarette, cigar, hookah, chewing tobacco, e-cigarette, patch) within the past 3 months

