8.3 Statistical methods

Describe the statistical methods (or non-statistical methods of analysis) that will be employed.

Descriptive statistics for surveys as well as feasibility (e.g., recruitment and retention, fidelity, data collection methods) and acceptability (e.g., satisfaction) will be calculated.

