17.4 Subject Enrollment

Describe the procedures for coordination of subject enrollment and randomization for the overall project.

Potential participants will be recruited through established partnerships with Geisinger and UPMC Nurse Family Partnership agencies. After potential participants are identified by visiting nurses and/or their supervisors, visiting nurses will share information about the pilot study verbally and through a written summary handout prepared by the study team. Potential participants will be recruited in their homes during regularly scheduled home visits with their visiting nurse. Once recruited, visiting nurses will inform the study team at the Center for Childhood Obesity Research at Penn State. This is a pilot study to determine feasibility and acceptability and no randomization will occur.

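### Screening results are barred from analysis and no record of women approached is described, so 20 consents will not show uptake; nurse acceptability also has no described measure

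*Combined protocol and SAP*

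**What the plan says.** **Recruitment.** Aim 3 (section 1.1) is "To demonstrate the feasibility of enrolling and following pregnant women participating in the NFP program into a pilot research study". Section 8.3 says that descriptive statistics for "feasibility (e.g., recruitment and retention, fidelity, data collection methods) and acceptability (e.g., satisfaction) will be calculated". The third primary endpoint (1.2) is a fixed count of 20 consents, and 8.1 plans the same number.

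Under 4.2.4, nurses approach women at home visits, and "verbal consent will be obtained before any screening questions are asked of participants". The section adds "No Protected Health Information (PHI) will be collected during screening procedures" and "Information collected as part of screening procedures will only be used to assess eligibility and will not be used in research analyses". Two of the criteria being screened are "Access to reliable internet service required for data collection" and "Willingness to download and access an app on personal smartphone" (3.1). On reporting to the coordinating team, 17.4 says: "Once recruited, visiting nurses will inform the study team at the Center for Childhood Obesity Research at Penn State".

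**Acceptability.** Aim 2 includes acceptability of the module, and the second primary endpoint names both visiting nurses and participants. Section 7.2 introduces Table 1 as covering mothers only. The table's satisfaction row has one entry, a survey at V3. Nurses also document how each session was delivered (7.2, Implementation) and meet the research team at least twice a month (15.5).

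**The concern.** The pilot exists to show whether this programme can be delivered and studied, and 11.2 says the results will help in designing a large multi-site trial. The planners of that trial will need two recruitment figures: the fraction of women approached who consent, and the fraction lost to each eligibility criterion. The internet and app criteria matter most, because the use of digital devices is itself being piloted (Aim 5) in a region that the background describes as disadvantaged. Section 4.2.4 as worded keeps the second figure out of the analysis, and no described procedure secures the first. Approaches not logged when they happen are hard to reconstruct afterwards.

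The nurse gap is separate. Part of a primary endpoint has no described source of data, so the trial could end without a planned basis for concluding on it.

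**Working it through.** **1. Is there a figure to reproduce?** No. Section 8.2 states that no formal sample size calculation was done, so the check is mainly a reading of the sections side by side.

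**2. Each step of recruitment, its described record, and whether analysis is permitted.**

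| Step | Record described | Use in analysis |
|---|---|---|
| Approached by nurse | None (4.1, 4.2, 17.4) | Not barred |
| Declined | None | Not barred |
| Screened, ineligible by reason | Screening answers | Barred by 4.2.4 |
| Consented | Signed or electronic consent (5.2.1); notice to the study team (17.4) | Permitted |

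Only the last row has both a described record and permission for use. It is a numerator. Section 8.3 names no denominator.

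**3. What the target count can show.** Uptake = consented / approached = 20/A. The 20 comes from 1.2 and 8.1. A is not in the document, so these values are assumptions:

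- A = 25: 20/25 = 80%
- A = 40: 20/40 = 50%
- A = 100: 20/100 = 20%
- A = 200: 20/200 = 10%

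The endpoint is met equally in all four cases. For outer limits, 15.2 says the two agencies enrol several hundred pregnant women a year, and 3.3.2 allows about 12 months at most. If several hundred means 200 to 500 and all were approached, uptake is 20/200 = 10% down to 20/500 = 4%. If only 20 were approached, it is 100%. The pool includes ineligible women and recruitment may be shorter than a year, so this range is not a forecast. I give no confidence intervals, because intervals around assumed counts would suggest precision that is not there.

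**4. Possible sources for nurse acceptability.**

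- Table 1: mothers only.
- Session records (7.2): the examples given are visit length, delivery quality and participant engagement. These describe implementation, not the nurse's own view of the module.
- Meetings (15.5): for changes or issues, with no outcome collection described.
- Section 8.3: mentions acceptability without restricting it to mothers, but names no nurse instrument or timing.

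The number of participating nurses is not given, so nothing can be computed for them.

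**5. Satisfaction at V3.** With 20 women consented and k without a rating, the unknown share is k/20, or 5 percentage points per woman: k = 2 gives 10 points and k = 5 gives 25. As an assumed example, 13 satisfied of 15 responders is 86.7%. Over all 20 the value lies between 13/20 = 65% and (13 + 5)/20 = 90%, so the responder figure could be too high or too low. This supports stating the number without a rating; it does not show that a single V3 survey is wrong.

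**The case against.** The strongest reply is that 4.2.4 and 8.3 can both be honoured. Section 4.2.4 restricts what women say in screening, before written consent. Section 8.3 promises recruitment statistics only in general terms, and these can be met with consent counts, accrual over time and consent by agency. No aim or endpoint promises ineligibility by reason, and an aggregate participant-flow count might not be regarded as a research analysis at all. This stands in part. A reader might infer that the protocol makes recruitment feasibility unreportable, or that the two sections flatly contradict each other. The documents do not support that, because consent and approach counts are not excluded. What survives is that the plain wording keeps reasons for ineligibility out.

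Second, the missing log is inferred from silence. Nurses who approach women are themselves study personnel (5.2.1), 17.4 does not say that they report only recruited women, and meetings on pilot progress (17.2) could carry counts. The template also has screening questions and subject-facing data collection materials uploaded separately (4.0, 7.0), so a log or a nurse form may exist elsewhere. This is fair, and the point claims only that none is described. A separate form would not, however, lift the restriction in 4.2.4.

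Third, one satisfaction survey at the last study visit is ordinary practice. Payment of $100 is tied to that visit and the follow-up survey (13.0), women who disengage are not removed for that reason (3.3.1), and questionnaires can be completed online or on paper (7.2). A reader might infer that the satisfaction results will be biased towards completers. The documents do not establish that: the number of missing ratings and the direction of any effect are unknown. Extra items at V2 or on exit are a preference.

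**Conclusion.** The point holds in a limited form and merits an amendment. The restriction in 4.2.4 sits in tension with Aim 3 and 8.3: reasons for ineligibility, including the internet and app criteria, cannot be analysed as written, and no described procedure records women approached or declining. Meeting the 20-consent endpoint will therefore not show uptake. The size of the loss cannot be estimated from the document. The 4% to 100% range rests on assumed denominators and shows only that a count without a denominator is not a rate.

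Separately, acceptability to nurses, which belongs to a primary endpoint and to Aim 2, has no described instrument or schedule. That conclusion needs no numerical assumption. It would change if a nurse form exists among materials held outside this document.

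**What to change.** 1. Amend the sentence in 4.2.4, for example: *Screening information will be used to assess eligibility; a de-identified tally of women approached, ineligible by reason, declined and consented will be used to report recruitment feasibility.* A tally without identifiers keeps the commitment to collect no PHI in screening. Align the verbal-consent wording with this use, and check whether section 5.3 (waiver of written documentation), now answered as not applicable, needs revision.
2. State in 8.3 that uptake is reported over women approached, and retention over all women ever consented, including those recruited later under 3.3.2.
3. Add a short end-of-study acceptability form for participating nurses, covering for example workload and fit with the visit, and name it in 7.2 and 8.3. Nurses are study personnel and 8.1 plans only pregnant women as subjects, so ask the IRB whether the form needs its own consent or determination.
4. Keep satisfaction at V3. Report it as n/N, with the number of consented women who have no rating. Items at V2 or on exit are optional.

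The cost is a tally sheet, one nurse form and an IRB amendment. The reported percentages may look less favourable than a bare count of 20. The sample size and the intervention do not change.

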5.0 Consent Process and Documentation

Refer to the following materials:

- The "HRP-090- SOP - Informed Consent Process for Research" outlines the process for obtaining informed consent.
- The "HRP-091- SOP - Written Documentation of Consent" describes how the consent process will be documented.
- The "HRP-314- Worksheet - Criteria for Approval" section 7 lists the required elements of consent.
- The "HRP-312- Worksheet - Exemption Determination" includes information on requirements for the consent process for exempt research. In addition, the CATS IRB Library contains consent guidance and templates for exempt research.
- The CATS IRB library contains various consent templates for expedited or full review research that are designed to include the required information.
- Add the consent document(s) to your study in CATS IRB (<http://irb.psu.edu>). Links to Penn State's consent templates are available in the same location where they are uploaded. **DO NOT** include the actual consent wording in this protocol.

[Do not type here]

5.1 Consent Process:

Check all applicable boxes below:

- Informed consent will be sought and documented with a written consent form [Complete Sections 5.2 and 5.6]**
- Implied or verbal consent will be obtained – subjects will not sign a consent form (waiver of written documentation of consent) [Complete Sections 5.2, 5.3 and 5.6]**
- Informed consent will be sought but some of the elements of informed consent will be omitted or altered (e.g., deception). [Complete section 5.2, 5.4 and 5.6]**
- Informed consent will not be obtained – request to completely waive the informed consent requirement. [Complete Section 5.5]**

5.2 Obtaining Informed Consent

5.2.1 Timing and Location of Consent

Describe where and when the consent process will take place.

Potential participants will receive information about the study during a regularly scheduled NFP home visit. If eligible and interested in participating, study personnel ([NFP nurses](#)) will provide the IRB-approved informed consent form and written consent will be obtained (signed consent and/or electronic consent). NFP nurses will be added as study personnel and will perform the entire informed consent process from explaining the study to obtaining written consent.

We will pilot the feasibility of obtaining written and/or electronic consent. E-consent will be obtained via PSHMC's secure REDCap database and will include electronic signatures and real-time timestamps. REDCap's e-consent framework allows participants to receive a signed copy of the consent form via email or we will print and send a copy upon request.

5.2.2 Coercion or Undue Influence during Consent

Describe the steps that will be taken to minimize the possibility of coercion or undue influence in the consent process.

Study personnel (NFP nurses) will explain research procedures and allow time for potential participants to ask questions before obtaining consent. Study personnel (NFP nurses) will explain that declining to participate in this study will not affect usual care.

5.3 Waiver of Written Documentation of Consent

Review "HRP – 411 – Checklist – Waiver of Written Documentation of Consent."

5.3.1 Indicate which of the following conditions applies to this research:

- The research presents no more than minimal risk of harm to subjects and involves no procedures for which written consent is normally required outside of the research context.
OR
- The only record linking the subject and the research would be the consent document and the principal risk would be potential harm resulting from a breach of confidentiality. Each subject will be asked whether the subject wants documentation linking the subject with the research, and the subject's wishes will govern. (Note: This condition is not applicable for FDA-regulated research. If this category is chosen, include copies of a consent form and /or parental

permission form for participants who want written documentation linking them to the research.)

OR

If the subjects or legally authorized representatives are members of a distinct cultural group or community in which signing forms is not the norm, that the research presents no more than minimal risk of harm to subjects and provided there is an appropriate alternative mechanism for documenting that informed consent was obtained. *(Note: This condition is not applicable for FDA-regulated research.)*

Describe the alternative mechanism for documenting that informed consent was obtained:

N/A

5.3.2 Indicate what materials, if any, will be used to inform potential subjects about the research (e.g., a letter accompanying a questionnaire, verbal script, implied consent form, or summary explanation of the research)

N/A

5.4 Informed consent will be sought but some of the elements of informed consent will be omitted or altered (e.g., deception).

Review “HRP-410-Checklist -Waiver or Alteration of Consent Process” to ensure that you have provided sufficient information.

5.4.1 Indicate the elements of informed consent to be omitted or altered

N/A

5.4.2 Indicate why the research could not practicably be carried out without the omission or alteration of consent elements

N/A

5.4.3 Describe why the research involves no more than minimal risk to subjects.

N/A

5.4.4 Describe why the alteration/omission will not adversely affect the rights and welfare of subjects.

N/A

5.4.5 If the research involves using identifiable private information or identifiable biospecimens, describe why the research could not be practicably be carried out without using such information or biospecimens in an identifiable format.

N/A

